7. ADVERSE EVENTS: LIST AND REPORTING REQUIREMENTS

Safety Evaluation Procedures

Adverse Event

An adverse event (AE) is any untoward medical occurrence in a subject administered a pharmaceutical product; such occurrence does not necessarily have a causal relationship with this treatment. An adverse event is, therefore, any unfavorable and unintended change in the structure, function, or chemistry of the body that is temporally associated with the use of the study drugs, whether or not considered related to the use of the product. Any worsening (i.e., any clinically significant adverse change in frequency and/or intensity) of a preexisting condition that is temporally associated with the use of the study drugs, is also an adverse event.

Adverse events may occur at any point during the study period, including pre-treatment, treatment and follow-up period as specified by the protocol.

Adverse events will be graded and recorded throughout the study period according to NCI CTCAE, version 4.0. Toxicities will be characterized in terms of duration, intensity, and time to onset. Safety endpoints will include all types of adverse events, in addition to laboratory safety assessments, ECOG performance status, ECGs, and vital signs.

The investigator must assess all abnormal laboratory results for their clinical significance. If any abnormal laboratory result is considered clinically significant, the investigator must provide details about the action taken with respect to the study drug, patient care, and outcome.

The following safety evaluations will be performed during patient screening and at defined points during the course of the study:

- Vital signs
- Laboratory tests, including complete blood count (CBC), serum chemistry, urinalysis, coagulation studies (PT/PTT, INR), pregnancy test, LDH
- Electrocardiograms (ECG)
- Physical examinations
- Performance Status Evaluation using the ECOG scale
- Adverse event monitoring using the NCI CTCAE v4.0

The STUDY CALENDAR (Section 10) provides specific details on collection time points.

Serious Adverse Events (SAE)

SAE as defined in the following FDA website will be reported to the FDA:

<http://www.fda.gov/Safety/MedWatch/HowToReport/ucm053087.htm>

Details are listed in the Appendix 8.

Comprehensive Adverse Events and Potential Risks Lists (CAEPRs)

The following adverse events were observed in patients treated with single agent TGR-1202 and were considered at least possibly related to study medication. See the TGR-1202 investigator brochure for a complete list of all adverse events reported regardless of causality.

Very Common ($\geq 10\%$) Blood and lymphatic system disorders: Neutropenia

Gastrointestinal disorders: Nausea, Diarrhea, Vomiting

General disorders and administration site conditions: Fatigue **Metabolism and nutrition disorders:** Decreased appetite **Skin and subcutaneous tissue disorders:** Rash

Common ($\geq 1\%$ and $< 10\%$)

Blood and lymphatic system disorders: Anemia, Febrile neutropenia, Leukocytosis, Thrombocytopenia

Ear and labyrinth disorders: Tinnitus

Eye disorders: Vision Blurred, Visual Acuity Reduced

Gastrointestinal disorders: Abdominal distension, Abdominal pain, Constipation, Dry mouth, Dyspepsia, Eruption, Hypoaesthesia oral, Mouth Ulceration, Flatulence, Gastroesophageal reflux disease, Paraesthesia oral, Colitis

General disorders and administration site conditions: Asthenia, Chills, Malaise, Oedema peripheral, Pyrexia, Mucosal inflammation **Hepatobiliary disorders:** Hyperbilirubinaemia

Infections and infestations: Candida infection, Lung infection, Oral candidiasis, Pneumonia, Upper respiratory tract infection, Sinusitis

Investigations: Alanine aminotransferase increased, Aspartate aminotransferase increased, Blood creatinine increased, Blood lactate dehydrogenase increase, Blood phosphorus increased, Blood sodium increased, Blood uric acid increased, International normalized ratio increased, Lymphocyte count increased, Weight decreased

Metabolism and nutrition disorders: Dehydration, Hyperglycaemia, Hyperlipidaemia, Hypertriglyceridaemia, Hypokalaemia, Hyponatraemia, Hypophosphataemia, Hypomagnesaemia

Musculoskeletal and connection tissue disorders: Arthralgia, Muscle spasms, Muscular weakness, Myalgia, Pain in extremity, Pain in jaw

Nervous system disorders: Dizziness, Dysgeusia, Headache, Memory impairment, Neuropathy peripheral, Somnolence, Tremor, Peripheral sensory neuropathy

Psychiatric disorders: Anxiety, Insomnia, Libido decreased, Delirium, Parasomnia

Reproductive system and breast disorders: Erectile dysfunction

Respiratory, thoracic and mediastinal disorders: Cough, Dyspnea, Epistaxis, Hypoxia, Respiratory failure, Sinus congestion

Skin and subcutaneous tissue disorders: Alopecia, Dermatitis acneiform, Night sweats, Pruritus

Vascular disorders: Hot flush

In addition to the preceding adverse events, the following adverse events occurred in patients administered TGR-1202 but were deemed by investigators to be unlikely related or not related to TGR-1202 therapy. Due to the low number of patients evaluable for safety at this time, however, TG Therapeutics cannot rule out these events occurring in future studies:

Liver Disorders: Elevated levels of certain liver enzymes

Brain and nerve related disorders: Paresthesia

Kidney disorders: Elevated blood urea nitrogen levels, Elevated phosphorus, Hyperuricemia

Breathing and chest related disorders: Nasal congestion, Upper respiratory tract infection

Infections and Infestations: Infection

Safety analyses

Safety evaluations will be based on the incidence, intensity, and type of adverse events, as well as on clinically significant changes in the patient's physical examination, vital signs, and clinical laboratory results. Safety analyses will be performed using the safety population. Safety variables will be tabulated and presented by the dose of TGR-1202 study drug actually received. Exposure to study treatment and reasons for discontinuation of study treatment will also be tabulated.

Adverse Event Characteristics

- **CTCAE term (AE description) and grade:** The descriptions and grading scales found in the revised NCI Common Terminology Criteria for Adverse Events (CTCAE) version 4.0 will be utilized for AE reporting. A copy of the CTCAE version 4.0 can be downloaded from the CTEP web site (<http://ctep.cancer.gov>).
- **‘Expectedness’:** AEs can be classified as ‘Unexpected’ or ‘Expected’ for expedited reporting purposes only.
- **Attribution** of the AE:
 - Definite – The AE is *clearly related* to the study treatment.
 - Probable – The AE is *likely related* to the study treatment.
 - Possible – The AE *may be related* to the study treatment.
 - Unlikely – The AE is *doubtfully related* to the study treatment.
 - Unrelated – The AE is *clearly NOT related* to the study treatment.

Expedited Adverse Event Reporting

The Principal Investigator agrees to provide appropriate parties with copies of all serious adverse events within two working days. Additionally, the Principal Investigator agrees to report any pregnancy occurring in association with use of TGR-1202 to the appropriate parties.

It is important to distinguish between “serious” and “severe” adverse events, as the terms are not synonymous. Severity is a measure of intensity; however, an AE of severe intensity need not necessarily be considered serious. For example, nausea which persists for several hours may be considered severe nausea, but may not be considered an SAE. On the other hand, a stroke which results in only a limited degree of disability may be considered only a mild stroke, but would be considered an SAE. Severity and seriousness should be independently assessed when recording AEs and SAEs on the eCRF.

Adverse events classified by the treating investigator as **serious** require expeditious handling and reporting to the Sponsor in order to comply with regulatory requirements. Serious adverse events may occur at any time from Cycle 1/Day 1 through the 30-day follow-up period after the last study treatment. Sponsor or designee should be notified of all SAEs, regardless of causality, within 24 hours of the first knowledge of the event by the treating physician or research personnel.

To report an SAE, see the appropriate form.

All SAEs (regardless of causality assessment) occurring on study or within 30 days of last study treatment should be immediately reported to the sponsor as SAEs within the CRF and followed until resolution (with autopsy report if applicable).

Progression or death due to disease progression should be reported by the investigator as a SAE only if it is assessed that the study drugs caused or contributed to the disease progression (i.e. by a means other than lack of effect). Unrelated events of disease progression should be captured on the appropriate CRF.

The investigator must review and sign off on the SAE data on the SAE report. The SAE should be reported to the Sponsor (or Sponsor designee). When an SAE is reported to the sponsor or designee, the same information should be entered on the CRF within 24 hours (1 business day). Transmission of the SAE report should be confirmed by the site personnel submitting the report. Follow-up information for SAEs and information on non-serious AEs that become serious should also be reported to the sponsor or designee as soon as it is available; these reports should be submitted using the appropriate SAE form.

Investigators should report SAEs and follow-up information to their responsible Institutional Review Board (IRBs)/Independent Ethics Committee according to the policies of the responsible IRB (Research Ethics Committee).

Sponsor SAE Reporting Requirements

Sponsor is responsible for reporting relevant SAEs to the competent authority, other applicable regulatory authorities, and participating investigators, in accordance with ICH guidelines, FDA regulations, and/or local regulatory requirements.

Sponsor is responsible for reporting unexpected fatal or life-threatening events associated with the use of the study drugs to the regulatory agencies and competent authorities within 7 calendar days after being notified of the event. The Sponsor will report all related but unexpected SAEs including non-death/non-life-threatening related but unexpected SAEs (SUSAR) associated with the use of the study medications to the regulatory agencies and competent authorities by a written safety report within 15 calendar days of notification. Following the submission to the regulatory agencies and competent authorities, Investigators and trial sites will be notified of the SUSAR. Investigators must report SUSARs and follow-up information to their responsible Institutional Review Board (IRBs)/Independent Ethics Committee according to the policies of the responsible IRB (Research Ethics Committee).

Report of Adverse Events to the Institutional Review Board (IRB)

Reportable information should always be reported by the PI directly to the IRB within 5 working days since the PI's first knowledge of the event or new information.

Investigator Reporting to the FDA

The investigator is responsible for reporting any SAEs to the FDA. SAEs that are **unlisted/unexpected, at least possibly related to the drug**, and that have not previously been reported in the Investigators brochure, or reference safety information document should be reported promptly to the Food and Drug Administration (FDA) by [contact]), fax ([name]), or via MedWatch Online. Fatal or life threatening SAEs that meet the criteria for reporting to the FDA must be reported to the FDA within 7 calendar days since first

awareness of the event. All other SAEs that meet the criteria for reporting to the FDA must be reported to the FDA within 15 calendar days since first awareness of the event. A clear description of the suspected reaction should be provided along with an assessment as to whether the event is drug or disease related.

Adverse event updates/IND safety reports

TG therapeutics shall notify the Investigator via an IND Safety Report of the following information:

- Any AE associated with the use of the drug in this study or in other studies that is both serious and unexpected.
- Any finding from tests in laboratory animals that suggests a significant risk for human subjects including reports of mutagenicity, teratogenicity, or carcinogenicity.

The Investigator shall promptly notify his/her IRB/ethics committee of these new serious and unexpected AE(s) or significant risks to subjects.

The Investigator must keep copies of all AE information, including correspondence with TG and the IRB/EC, on file.

Expedited Reporting Guidelines

Note: All deaths on study require expedited reporting regardless of causality. Attribution to treatment or other cause must be provided.

Expedited AE reporting timelines defined:

- “1 business day; 5 calendar days” – The investigator must *initially* report the AE within 1 business day of learning of the event followed by a complete report within 5 calendar days of the initial 24-hour report.
- “10 calendar days” - A *complete* report on the AE must be submitted within 10 calendar days of the investigator learning of the event.
- Any medical event equivalent to CTCAE grade 3, 4, or 5 that precipitates hospitalization (or prolongation of existing hospitalization) must be reported regardless of attribution and designation as expected or unexpected with the exception of any events identified as protocol-specific expedited adverse event reporting exclusions.
- Any event that results in persistent or significant disabilities/incapacities, congenital anomalies, or birth defects must be reported if the event occurs following treatment.

Protocol-Specific Expedited Adverse Event Reporting Exclusions

For this protocol, certain AEs/grades are exceptions to the Expedited Reporting Guidelines and do not require expedited reporting. The following AEs must be reported through the routine reporting mechanism:

Table 2: CTCAE AE Reporting Exclusions

CTCAE Category	Adverse Event	Grade	Hospitalization / Prolongation of Hospitalization	Attribution
Blood/Bone Marrow	Neutropenia <7 days without fever	4	No	Yes
Blood/ Bone Marrow	Thrombocytopenia <7 days without bleeding	4	No	Yes

Pregnancy on Study

During the course of the study, all female patients of childbearing potential (the definitions of “women of childbearing potential” are listed in Appendix 4) must contact the treating investigator immediately if they suspect that they may be pregnant (a missed or late menstrual period should be reported to the treating investigator).

If an investigator suspects that a patient may be pregnant prior to administration of study drug(s), the study drug(s) must be withheld until the result of the pregnancy test is confirmed. If a pregnancy is confirmed, the patient must not receive any study drug(s), and must be discontinued from the study.

If an investigator suspects that a patient may be pregnant after the patient has been receiving study drug(s), the study drug(s) must immediately be withheld until the result of the pregnancy test is confirmed. If a pregnancy is confirmed, the study drug(s) must be immediately and permanently stopped, the patient must be discontinued from the study, and the investigator must notify the Study Chair or Medical Monitor as soon as possible.

If a patient becomes pregnant while enrolled in the study, an SAE form should be completed and submitted to the Sponsor. Abortions (spontaneous, accidental, or therapeutic) must also be reported to the Sponsor.

Congenital anomalies/birth defects always meet SAE criteria, and should therefore be expeditiously reported as an SAE, using the previously described process for SAE reporting.

Study Drug Overdose

Symptomatic and non-symptomatic overdose must be reported in the eCRF. Any accidental or intentional overdose with the study treatment (TGR-1202) that is symptomatic, even if not fulfilling a seriousness criterion, is to be reported to the Sponsor immediately (within 24 hours) using the corresponding SAE form, and following the same process described for SAEs. If a study drug overdose occurs, patients should stop study drug dosing and be clinically monitored as appropriate, managing symptoms/side effects that may occur.

Secondary Malignancy

Any secondary malignancy event must be reported via the SAE form (in addition to the routine AE reporting mechanisms). Any malignancy possibly related to cancer treatment should also be reported via the routine reporting mechanisms outlined in the protocol.

Routine Adverse Event Reporting

All Adverse Events **must** be reported in routine study data submissions. New onset adverse events occurring up to 30 days after study completion or patient withdrawal will be captured. All new AEs occurring during this period must be reported and followed until resolution unless, in the opinion of the investigator, these values are not likely to improve because of the underlying disease. In this case, the investigators must record his or her reasoning for this decision in the patient's medical record and as a comment on the CRF. Follow up of these events will be performed according to the same procedures as described above for AEs observed during the study period.

After 30 days, only AEs, SAEs, or deaths assessed by the investigator as treatment related are to be reported.

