 - c. Symptomatic or documented congestive heart failure that meets New York Heart Association (NYHA) Class III to IV definitions (see Appendix 6);
 - d. History of stroke within the last 6 months prior to screening

Inclusion of Women and Minorities

Both men and women of all races and ethnic groups are eligible for this trial.

Treatment Plan

Patients will be treated with TGR-1202 at a dose of 800 mg daily from day 1 to 28 on a 28-day cycle.

Duration of Treatment

Patients will be treated until one of the following events occurs:

- Disease progression
- Unacceptable adverse event(s)
- Withdrawal of consent
- Changes in the patient's condition that render continuation of the study drug unacceptable in the judgment of the treating physician
- An event that in the judgment of the treating physician warrants discontinuation of therapy.
- Patient withheld study drug for >28 days

Sample Size

The study will accrue a total of up to approximately **20 patients**.

Safety

Patients will be monitored carefully for the development of AE. AE will be evaluated according to criteria outlined in the National Cancer Institute (NCI) Common Terminology Criteria for Adverse Events (CTCAE), version 4.0.

Efficacy Outcome

Patients will be monitored for clinical and/or radiographic evidence of disease response. Response will be evaluated using clinical parameters, CT or PET/CT scan (PET/CT scan is preferred), and bone marrow or other tissue biopsy, according to the *Updated Recommendations for Evaluation, Staging, and Response Assessment for Hodgkin and Non-Hodgkin Lymphoma: The Lugano Classification.* (Cheson et al., 2014b)

Figure 1: Study Plan Flow Chart

[figure not shown]

Figure 2. Pharmacokinetics (PK) schedule

Pharmacokinetic studies

Cycle 1, days 1 and 15; cycle 2 , day 15; cycle 4, day 15

[figure not shown]
[figure not shown]

Figure 3. Pharmacodynamic (PD) Schedule

Pharmacodynamic studies on peripheral blood*

Cycle 1, days 1 and 15; cycle 2, day 15; cycle 4, day 15

Pharmacodynamic studies on tumor cells, blood cells, and buccal fibroblasts*

Screening, Cycle 2, day 15 (mandatory); cycle 4, day 15 (optional); end of treatment/POD (optional)

[figure not shown]
[figure not shown]

Figure 4. Study schema

¹ Includes tumor cells, blood cells, and buccal fibroblasts; tumor tissue includes nodal or extranodal tumor tissue that can be visualized and/or palpated + bone marrow aspiration and biopsy if bone marrow positive for lymphoma; ²

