6. DOSING DELAYS/DOSE MODIFICATIONS

- For a new treatment cycle to begin, patients must meet the criteria outlined in section 5. Moreover, all other toxicity must have returned to grade ≤ 2 . If either of these conditions are not met, the study drug will be held.
- If interruption of study drug lasts for more than 28 days, treatment should be discontinued and the subject should be removed from the study (please contact the study chair to discuss longer interruptions).
- Patients who experience toxicity and require the study drug to be withheld may not be candidates for biopsy. Patients who miss 4 or more doses of drug prior to a planned biopsy should be considered ineligible for biopsy. The treating physician will make the ultimate decision in this regard.

Dose Modifications

Patients will be monitored continuously for toxicity while on study therapy. Toxicity will be assessed using the NCI CTCAE v4.0 (<http://evs.nci.nih.gov/ftp1/CTCAE/CTCAE>) grading scale. If a patient has an adverse event of particular severity or had an adverse event at least possibly related to study drug, then dose modifications will be made according to the guidelines.

Deviations from these guidelines may occur only if agreed upon by the Principal Investigator. There should be no attempt to make up for doses omitted due to toxicity.

A maximum four (4) week delay of treatment for recovery from toxicity is allowed to recover from hematologic toxicities to \leq Grade 3 or non-hematologic toxicities to \leq Grade 2 or to baseline level. If greater than a four (4) week delay is necessary, then the patient should discontinue treatment

and continue to be followed for progression. If a patient withdraws consent or has documented progression, an end of study visit should be completed.

Recommended treatment interruptions/holds or dose modifications are summarized below and may be based on the clinical judgment of the Investigator with notification to the Principal Investigator. For an individual patient, dose reductions and discontinuations may be more conservative than indicated. (i.e., to dose-reduce or discontinue for non-hematologic toxicity of lower grades) based on the clinical judgment of the Investigator with notification to the Medical Monitor/Sponsor.

Summary of Dose Holds for Treatment-Related Toxicities

NCI-CTCAE Grade	Dose Delay and/or Modification
Hematologic Adverse Event	
Neutropenia	
Grade ≤ 2 neutropenia	Maintain current dose. Consider supportive care as warranted.

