Grade 3 neutropenia	Maintain current dose, consider supportive care. If recurrence or persistent Grade 3, the next lower dose level will be allowed.
Grade 4 neutropenia or occurrence of neutropenic fever or infection	Delay TGR-1202 until Grade ≤ 3 and/or neutropenic fever or infection is resolved; thereafter, resume at full dose. Consider supportive care. If delay is > 4 weeks discontinue study drug. If recurrence after rechallenge, resume at the next lower dose level at discretion of the investigator.
Thrombocytopenia	
Grade ≤ 3 thrombocytopenia	Maintain current dose level and provide supportive care as clinically warranted.
Grade 4 thrombocytopenia	Delay TGR-1202 until Grade ≤ 3 ; thereafter, resume at full dose. Consider supportive care intervention as warranted. If delay is > 4 weeks, discontinue TGR-1202. If recurrence after rechallenge, resume at the next lower dose level.
Pulmonary & Related Infections*	
Grade ≥ 2	Withhold TGR-1202 as warranted, provide supportive care. Resume at full dose. If recurrence after rechallenge, resume at the next lower dose level.
*While pneumonitis has been minimal with TGR-1202, it is a reported adverse event associated with other PI3K delta inhibitors. PCP and anti-viral prophylaxis is required for any study patient.	
All Other Non-Hematological Adverse Events	
Grade ≤ 2	Maintain current dose level

Grade ≥ 3	Withhold TGR-1202 until Grade ≤ 2 . Resume at full dose. If recurrence after rechallenge, resume at the next lower dose level.
----------------	--

Study Drug Dose Levels

Study Drug	Starting Dose	1 st Dose Reduction	2 nd Dose Reduction
TGR-1202	800 mg	600 mg	400 mg

If a patient requires a dose reduction of TGR-1202 due to study drug related toxicity, the dose may not be re-escalated. If further evaluation of the toxicity reveals the event was not related to TGR-1202, this must be recorded in the medical record and dose re-escalation to the next higher dose level may be considered at the discretion of the investigator.

Ordering TGR-1202

Once the clinical study site receives regulatory approval (IRB/IEB), and the Sponsor and/or Sponsor designee performs the Site Initiation Visit and inspection of pharmacy, and determines the site to be officially open for enrollment, and once a patient is identified, a shipment of predetermined quantity of TGR-1202 will be shipped to the clinical study site.

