11. MEASUREMENT OF EFFECT

The primary objective of this study is to evaluate the ORR of the study drug. Patients with measurable disease will be assessed by standard criteria. Patients will be re-evaluated at the end of cycle 2 and cycle 6, thereafter every 4 months, or every 6 months if a CR is achieved. Response will be evaluated with physical exam, computerized tomography (CT) and tissue biopsies as defined in the 2014 Lugano classification.(Cheson et al., 2014b) PET/CT is optional, but strongly encouraged.

Evaluation of response:

Definitions

Evaluable for toxicity: All patients will be evaluable for toxicity starting from Day 1 of Cycle 1.

Evaluable for objective response: Patients who have received at least 1 cycle of therapy, and have had their disease re-evaluated will be considered evaluable for response. These patients will have their response classified according to the definitions stated below (Table 3). Patients who exhibit objective disease progression prior to the end of cycle 1 will also be considered.

Disease Parameters

Measurable disease. Measurable lesions are defined as those that can be accurately measured in two dimensions (longest diameter to be recorded) as ≥ 20 mm with conventional techniques (PET/CT, MRI, x-ray) or as ≥ 10 mm with spiral CT scan. All tumor measurements will be recorded in millimeters (or decimal fractions of centimeters). Tumor volume will be recorded as the sum of the product of the diameters (SPD) of the largest predominant target lesions (for sites of measurable disease, see Appendix 7).

FDG avidity is based on comparison with background tissues. There is no specific SUV cut-off value that is considered indicative of response.

Non-measurable disease (evaluable disease). All other lesions (or sites of disease), including small lesions (<10 mm using spiral CT scan), are considered non-measurable disease. Bone lesions, ascites, pleural/pericardial effusions, lymphangitis cutis/pneumonitis, inflammatory breast disease, abdominal masses (not followed by CT or MRI), and cystic lesions are all nonmeasurable.

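### Safety is to be tabulated by dose received, but every patient starts at 800 mg and lower dose levels arise from toxicity, so the dose rows are confounded by the outcome they report

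*Combined protocol and SAP*

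**What the plan says.** Section 7 (Safety analyses) contains the only instruction on tabulating safety; Section 13 adds none.

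- **Measure:** "Safety evaluations will be based on the incidence, intensity, and type of adverse events", together with clinically significant changes in examination, vital signs and laboratory results.
- **Analysis set:** "Safety analyses will be performed using the safety population". That population is not defined. Section 11 says "All patients will be evaluable for toxicity starting from Day 1 of Cycle 1", but this is an evaluability rule and specifies no table.
- **Presentation:** "Safety variables will be tabulated and presented by the dose of TGR-1202 study drug actually received". Exposure and reasons for discontinuation are also to be tabulated.

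There is one assigned dose. The synopsis says "Patients will be treated with TGR-1202 at a dose of 800 mg daily from day 1 to 28 on a 28-day cycle", and Section 5 agrees on the daily dose. Lower levels appear only in Section 6, as first and second reductions to 600 and 400 mg:

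- For pulmonary events and other non-haematological events above the stated grade: "Resume at full dose. If recurrence after rechallenge, resume at the next lower dose level".
- For Grade 3 neutropenia: "If recurrence or persistent Grade 3, the next lower dose level will be allowed".
- Earlier reduction on clinical judgement is also possible: "For an individual patient, dose reductions and discontinuations may be more conservative than indicated".

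After a reduction for drug-related toxicity the dose may not go back up. It may if the event is later found unrelated to the drug.

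**The concern.** In a trial that assigns patients to several doses, tables by dose received are natural. Here dose is not assigned but follows from what happens to the patient. A patient appears below 800 mg mainly because he or she had an adverse event, so a row defined by dose is partly defined by the outcome that the row reports.

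The plan leaves open whether a patient belongs to the lowest, last or average dose, or whether each event belongs to the dose taken at its onset. These choices give different incidences from the same data, and no all-treated column is named to anchor them.

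The synopsis lists the safety profile among the secondary objectives (Section 1 lists only dose delays and reductions). Section 2 argues that the drug is better tolerated than others in its class. The incidence among patients started at 800 mg is the figure a reader would carry into that comparison, and it should not depend on an unstated grouping rule.

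**Working it through.** **Plan's own figures.** The documents give no adverse-event incidence or reduction rate for this trial, so there is no safety figure to reproduce. The one design figure, 87% power for a response rate of 0.33 against 0.60 with 20 patients, does reproduce: success at 10 or more responses gives exact one-sided alpha 0.0866 and power 0.8725. It has no bearing on this point.

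**Inputs.** N = 20 (Section 13). Let a be the number of patients with at least one event of the kind that can prompt a reduction, and r ≤ a the number of those later reduced. Both a and r are assumptions.

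**Reading A: each patient is classed by lowest or last dose.** The all-treated incidence is a/20. The 800 mg row loses the r reduced patients from numerator and denominator and becomes (a−r)/(20−r). The reduced rows are r/r = 100% for the triggering events, by construction.

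| a | r | All treated | 800 mg row | Reduced rows |
|---|---|---|---|---|
| 6 | 1 | 6/20 = 30% | 5/19 = 26.3% | 1/1 |
| 6 | 3 | 6/20 = 30% | 3/17 = 17.6% | 3/3 |
| 6 | 6 | 6/20 = 30% | 0/14 = 0% | 6/6 |
| 8 | 4 | 8/20 = 40% | 4/16 = 25.0% | 4/4 |
| 10 | 3 | 10/20 = 50% | 7/17 = 41.2% | 3/3 |

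The case r = a is an extreme. Section 6 mostly returns a patient to full dose after a first event, so patients with a single event usually stay in the 800 mg row.

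**Reading B: each event is placed at the dose taken at onset, with all patients exposed at that dose as denominator.** All 20 start at 800 mg, and the first and triggering events happen there, so the 800 mg row stays at a/20. The reduced-dose rows contain only patients already selected for toxicity.

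**Both readings under a simple model.** Assume 12 cycles, an event hazard of 0.05 per patient-cycle, reduction at the second event, and the same hazard after reduction (no dose effect at all). The model was simulated with equal patients and with exponentially distributed differences in hazard between patients.

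| Quantity | Equal patients | Patients differ |
|---|---|---|
| All-treated incidence | 45.1% | 37.6% |
| Reading A, 800 mg row | 37.4% | 27.4% |
| Reading A, reduced rows | 100% | 100% |
| Reading B, 800 mg row | 45.1% | 37.6% |
| Reading B, reduced rows, crude incidence | 19.2% | 37.5% |
| Reading B, events per patient-cycle, 800 mg | 0.050 | 0.046 |
| Reading B, events per patient-cycle, reduced | 0.049 | 0.121 |

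The first column can be checked by hand. Over 12 cycles the expected count is 12 × 0.05 = 0.6. P(any event) = 1 − exp(−0.6) = 45.1% and P(two or more) = 1 − 1.6 × exp(−0.6) = 12.2%. The reading A row is then (45.1 − 12.2)/(100 − 12.2) = 37.5%, against 37.4% simulated.

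Under reading B the crude incidence at reduced doses is not above that at 800 mg. Once patients differ in susceptibility, the rate per patient-cycle is 0.121 against 0.046, although the simulated drug effect is identical at both doses. That difference is selection.

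**The case against.** A reader might infer that the 800 mg incidence will be understated and that the lowest doses will look the most toxic. The documents do not support this as a certainty. Section 7 does not say that patients are classed by their reduced dose. The exact dose and date are recorded (Section 5) and so is time to onset (Section 7), so classification by dose at onset is equally open. Under it, first and triggering events remain at 800 mg and crude incidence at reduced doses need not be higher. Nor do the documents say that a lower dose follows only recurrent or persistent toxicity: Section 6 allows earlier reduction on clinical judgement, and missed doses can also lower the dose received. These objections stand, and they make the consequences conditional.

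It can also be said that the table is descriptive, that no test or decision rests on it, that a total column is not excluded, and that under reading A the total can be recovered by adding rows (4/16 and 4/4 give 8/20). This limits the harm but does not remove it. Under reading B a patient can appear in more than one row, and an event type that first appears after a reduction is absent from the 800 mg row. The incidence for patients started at 800 mg then cannot be obtained by adding rows. A total column that is merely permitted is not planned.

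**Conclusion.** The point holds in conditional form. A by-dose safety presentation is confounded by toxicity, because lower dose levels come from reductions that toxicity prompts.

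- **Patients classed by lowest or last dose:** the 800 mg incidence is understated whenever at least one patient with the event is reduced and some patients have no event. With assumed counts the drop runs from 30% to 26.3% (one reduction among six affected patients) to 30% to 0% (all six reduced). Eight affected patients with four reductions gives 25% against 40%.
- **Events placed at dose at onset:** the 800 mg incidence of first and triggering events is not understated, but the reduced-dose rows are a selected group and should not be compared with the 800 mg row.

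The sizes rest on assumed event and reduction counts and, for the rates per cycle, on an assumed model. The direction under each reading does not depend on the particular counts chosen. The primary response analysis is unaffected. The change should be made because the stated presentation is misleading on the first reading and uninformative about dose on the second.

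**What to change.** Replace the by-dose sentence in Section 7 (Safety analyses) with:

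> Safety will be tabulated for all patients who received at least one dose of TGR-1202, as a single group, as the main presentation; events by dose at onset, with exposure time at each dose, will be a descriptive supplement only.

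This also supplies the missing definition of the safety population. The cost is one sentence. Dose, dates and time to onset are already to be recorded, so no data are added, and no dosing or reduction rule is touched.
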